4.4.1.2.6 Serious Adverse Event (SAE)

SAEs will be analyzed throughout the study using the following periods:

- During post-Dose 1 period (i.e., between injection 1 and injection 2), and during 21 days after the last injection
- During the 6-month follow-up period
- During the 12-month follow-up period

- During the study (i.e., all SAEs occurred during the study)

Additionally, a table will present all SAEs during the study in order to count all SAE collected.

Note: SAE that occurred before vaccination (negative time of onset) will not be included in analysis, but will be listed separately.

Safety analysis will include only those SAEs with time of onset before a participant received a non-study authorized/approved COVID-19 vaccine, if applicable. SAEs with time of onset on or after the date of receiving a non-study authorized/approved COVID-19 vaccine will be listed separately.

4.4.1.3 Laboratory test Results

Biological safety tests (biochemistry and hematology) will be performed at local laboratory. Biological endpoints will be assessed on samples taken at screening, V01, V02 (Cohort 1), V03 (Cohort 2), and unscheduled visits based on investigator's judgment, in cases of abnormal safety laboratory results.

The parameters to be evaluated will include serum chemistries (blood urea nitrogen (BUN), potassium, Aspartate Aminotransferase (AST)/serum glutamic-oxaloacetic transaminase (SGOT), total and direct bilirubin, creatinine, sodium, alanine aminotransferase (ALT)/ serum glutamic-pyruvic transaminase (SGPT), total protein, glucose (nonfasting), alkaline phosphatase, lipase, amylase; hematology (platelet count, hemoglobin, hematocrit, white blood cell (WBC) count with differential, neutrophils, lymphocytes, monocytes, eosinophils, basophils); and Urinalysis (Specific gravity, pH, glucose, protein, blood, ketones, bilirubin, urobilinogen, nitrite, leukocyte esterase by dipstick, microscopic examination). The microscopic examination will be done if blood or protein is abnormal.

Endpoints will be defined as either within or outside normal range. Normal ranges for each endpoint will be provided by the study center. The biological safety information will be entered by the site staff in the appropriate CRF forms along with units and normal ranges. In case of out-of-range values, specific endpoints may be rechecked and additional biological parameters may be evaluated, based on the Investigator's judgement. This complementary safety information will also be entered by the site staff in the appropriate CRF forms along with units and normal ranges.

Any change in the testing equipment using different ranges should be reported on an ongoing basis to the Sponsor so that any value can be interpreted at a given time against the appropriate range of values.

Biological safety endpoints will be assessed on whether or not they reach the pre-defined intensity levels (Grade 1, 2, or 3) for analytes with applicable toxicity grading, as specified in the protocol. Table 10.4 of the protocol contains the pre-defined intensity scales according to which the biological safety parameters will be assessed. If at least one of these intensity levels is reached, the Investigator will evaluate the clinical significance of the results and report clinically significant abnormal values as AEs in the CRF.

4.4.1.4 Other Safety Endpoints

4.4.1.4.1 Pregnancy

This information will be listed as collected. No derivation or imputation will be done.

4.4.1.4.2 Action Taken

Solicited injection site/systemic reactions after any vaccine injection(s) will be summarized, by action taken.

4.4.1.4.3 Seriousness

This information will be summarized as collected. No derivation or imputation will be done.

4.4.1.4.4 Outcome

This information will be summarized as collected. No derivation or imputation will be done.

4.4.1.4.5 Causality

This information will be summarized as collected. Missing causality (relationship) will be handled as described in Section 5.3.1.2.

4.4.1.4.6 AEs Leading to Study Discontinuation

A flag will be available in the clinical database for all AEs in order to identify AEs leading to discontinuation.

In general, the items that are counted are:

- For subject disposition: if subject did not complete the study due to AE as recorded in Completion at End of Study form
- For safety overview: if subject did not complete the study due to AE as recorded in Completion at End of Study form or had any solicited or unsolicited AEs causing study discontinuation / termination as recorded in solicited reaction or unsolicited AE forms within the time period indicated
- For summary of unsolicited AEs by system organ class (SOC) / PT: A solicited AE that has “Caused Study Termination” checked that is at least Grade 1 or an unsolicited AE that has “Caused Study Termination” checked that is at least Grade 1 or missing and is within the time period indicated

4.4.1.4.7 AESI

AESIs (serious and non-serious) will be collected throughout the study to ensure that events are communicated to the Sponsor in an expedited manner and followed-up until the end of the follow-up period or resolution, as per the assigned causality.

Anaphylactic reactions, generalized convulsions, thrombocytopenia, dry eyes, tearing, dry mouth, NOCMCs and pIMDs.

NOCMCs

NOCMCs are defined as any new ICD-10 diagnosis (10th revision of the International Statistical Classification of Diseases and Related Health Problems) that is applied to the participant during the course of the study, after receipt of the study agent, that is expected to continue for at least 3 months and requires continued health care intervention.

pIMDs

Potential immune-mediated diseases (pIMDs) are a subset of AEs that include autoimmune diseases and other inflammatory and/or neurologic disorders of interest which may or may not have an autoimmune etiology. AEs that need to be recorded and reported as pIMDs include those listed in Table 10.5 of the protocol.

AESIs will be analyzed throughout the study using the following periods:

- During post-Dose 1 period (i.e., between injection 1 and injection 2), and during 21 days after the last injection
- During the 6-month follow-up period
- During the 12-month follow-up period
- During the study (i.e., all AESIs occurred during the study)

Safety analysis will include only those AESIs with time of onset before a participant received a non-study authorized/approved COVID-19 vaccine, if applicable. AESIs with time of onset on or after the date of receiving a non-study authorized/approved COVID-19 vaccine will be listed separately.

4.4.1.4.8 Medically Attended AE (MAAE)

An MAAE is a new onset or a worsening of a condition that prompts the participant to seek unplanned medical advice at a physician's office or Emergency Department. Physician contact made over the phone or by e-mail will be considered a physician office visit for the purpose of MAAE collection. This includes medical advice seeking during the study visit or routine medical care. This definition excludes pediatric check-ups, follow-up visits of chronic conditions with an onset prior to entry in the study, and solicited reactions.

MAAE will be analyzed during the following time periods:

- During post-Dose 1 period (i.e., between injection 1 and injection 2), and during 21 days after the last injection
- During the 6-month follow-up period
- During the 12-month follow-up period
- During the study (i.e., all MAAEs occurred during the study)

Safety analysis will include only those MAAEs with time of onset before a participant received a non-study authorized/approved COVID-19 vaccine, if applicable. MAAEs with time of onset on

or after the date of receiving a non-study authorized/approved COVID-19 vaccine will be listed separately.

4.4.2 Immunogenicity

4.4.2.1 Computed Values for Analysis

In order to appropriately manage extreme values (< lower limit of quantification (LLOQ)) for analysis purposes, the following computational rule is applied to the values provided in the clinical database for each blood sample (BL) drawn:

- If a value is < LLOQ, then use the computed value LLOQ/2.
- If a value is \geq LLOQ, then use the value.

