As a precautionary step, a Sentinel Safety Cohort of 6 participants (younger adults only) within each dosing group from Cohort 1 will be enrolled. An ESDR will be performed, including evaluation of safety data and laboratory measures to D09 in Cohort 1 among younger adults 18-49 years of age. Upon acceptable safety demonstrated from unblinded review by limited members of the Sponsor Study Team (RMO, Biostatistician and Programmer, Pharmacovigilance Science Expert, and Global Safety Officer), the remaining participants in Cohort 1 and all participants in Cohort 2 will be enrolled. A non-clinical toxicology study in New Zealand White Rabbits is planned and will provide rabbit first-dose safety data prior to initiation of human clinical testing. Additional non-clinical safety evaluations will proceed in parallel to this human clinical trial.

Data up to D43, in addition to preclinical data, will support the selection of a formulation or formulations and dosing schedule to proceed to further testing in Phase III.

Rationale for Injection Schedule

In the setting of a pandemic, a single injection would be ideal to be able to protect vaccinees as early as possible and better manage vaccine supply. However, given the lack of pre-existing immune responses to SARS-CoV-2, it is most likely that 2 injections may be necessary.

A separation of 21 days for the 2-injection schedule is proposed for this program, mirroring the schedule that was evaluated and approved for pandemic influenza vaccines to address the 2009 H1N1 influenza pandemic (AS03 adjuvanted vaccines Pandemrix™, Arepanrix™; and AF03 adjuvanted Humenza vaccine). This schedule results in a second injection of the vaccine being administered earlier than with other common vaccines with longer separations between injections (ie, 28 days), thus aiming at earlier generation of potentially protective immune responses. This may be of particular interest in an ongoing pandemic setting.

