9.4.2 Primary Endpoints

9.4.2.1 Immunogenicity

The primary endpoints for the evaluation of immunogenicity are based on neutralizing antibody titers, which will be measured with the neutralization assay. The statistical analyses that will be performed for the following primary endpoints are as presented in [Table 3.1](#).

Pre-vaccination titers at < LLOQ will be converted to half LLOQ.

The 95% CIs for the GMTs/GMCs and GMT ratios will be calculated using normal approximation of log-transformed titers. The 95% CIs for the proportions will be based on the Clopper-Pearson method. The ratios of GMTs will be obtained between groups with the 95% CIs calculated using normal approximation of log-transformed titers. The differences in the seroconversion rates between groups will be computed along with the 2 sided 95% CIs by the Wilson-Score method without continuity correction. Additional parameters may be displayed as appropriate.

Additionally, to evaluate independent determinants of primary immunogenicity endpoints, regression models may be constructed for GMT titers and occurrence of neutralizing antibody seroconversion. When the outcome/dependent variable is a continuous numerical variable, linear models may be utilized; when the outcome/dependent variable is a categorical variable, logistic regression models may be utilized. Explanatory/independent variables inserted in these models would include age group (18-49 years, \geq 50 years), antigen dose level (low or high), and adjuvant (none, AS03, AF03). Models evaluating antibody titers or rates at D36 as the outcome variable would include also an explanatory variable corresponding to the injection schedule (1-injection, 2-injections). Multiplicative interaction terms will be included in expanded models to assess for evidence of effect modification. Non-significant interaction terms can be removed from the models.

Immunogenicity analyses will be performed on PPAS-IAS, unless otherwise specified.

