Additionally, to evaluate independent determinants of primary immunogenicity endpoints, regression models may be constructed for GMT titers and occurrence of 4-fold rise in serum neutralization titer relative to D01 at D22 for cohort 1 and D36 for cohort 2. When the outcome/dependent variable is a continuous numerical variable, linear models may be utilized; when the outcome/dependent variable is a categorical variable, logistic regression models may be utilized. Explanatory/independent variables inserted in these models would include age group (18-49 years, ≥ 50 years), antigen dose level (low-dose, high-dose), and adjuvant (none, AS03, AF03). Models evaluating antibody titers or rates at D22 for cohort 1 and D36 for cohort 2 as the outcome variable would include also an explanatory variable corresponding to the injection schedule (1-injection, 2-injections). Multiplicative interaction terms will be included in expanded models to assess for evidence of effect modification. Non-significant interaction terms with critical value < 0.05 can be removed from the models.

For descriptive purposes, the statistics presented on [Table 5.1](#) will be produced.

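### If about half or more of the one-injection titres fall below LLOQ, the optional linear models on LLOQ/2 values would usually understate dose and adjuvant effects and could show spurious schedule interactions; no censored-data model is planned

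*SAP*

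**What the plan says.** SAP 4.4.2.1 sets the rule "If a value is < LLOQ, then use the computed value LLOQ/2" and gives its scope: "the following computational rule is applied to the values provided in the clinical database for each blood sample (BL) drawn". Post-vaccination titres are therefore included. Protocol 9.4.2.1 is narrower: "Pre-vaccination titers at < LLOQ will be converted to half LLOQ". SAP 5.7 does not list the wider scope as a change.

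SAP 5.1.1.4 then says that "regression models may be constructed for GMT titers and occurrence of 4-fold rise in serum neutralization titer relative to D01", and "When the outcome/dependent variable is a continuous numerical variable, linear models may be utilized". The factors are age group, dose level, adjuvant and injection schedule, with the outcome taken at D22 for Cohort 1 and D36 for Cohort 2. On interactions: "Multiplicative interaction terms will be included in expanded models to assess for evidence of effect modification", and "Non-significant interaction terms with critical value < 0.05 can be removed from the models". Protocol 9.4.3.1 allows the same models for the secondary immunogenicity endpoints.

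Neither document names a censored-data model for these regressions, or a sensitivity analysis to the substituted value. The only alternative to half-LLOQ in a model is in SAP 5.1.2.4, where the correlates-of-risk analysis may use titre quantiles instead.

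**The concern.** Substituting one constant removes all variation below LLOQ. Where many titres lie there, a shift in the true mean moves the analysed mean by less than it should. Where nearly all titres are measured, the shift comes through in full. A dose or adjuvant effect of equal size on the log scale in both schedules would then look smaller in the schedule with more values below LLOQ, and a linear model would report the gap as an interaction.

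Unequal shares are plausible here. Participants are seronegative at entry, and of a single injection Protocol 4.2 says "it is most likely that 2 injections may be necessary". The SAP model also sets the titre 21 days after one injection against the titre 14 days after two.

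What is at stake is a misleading statement about whether dose and adjuvant effects depend on schedule, and an understated estimate of those effects after one injection.

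**Working it through.** **Inputs from the documents.** Summing Protocol Table 4.2 over the adjuvanted arms reproduces the pooled sizes in Protocol 9.2:
- schedule: 80 + 40 = 120 (one injection) and 160 + 80 = 240 (two)
- dose: 120 + 60 = 180 for each level
- adjuvant: AS03 160 + 80 = 240, AF03 80 + 40 = 120
- total: 360 adjuvanted + 20 unadjuvanted + 60 placebo = 440

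The cells are 60/60/120/120 for dose by schedule. For adjuvant by schedule they are AF03 60 and AS03 60 after one injection, and AF03 60 and AS03 180 after two.

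**Assumptions.** The documents give no LLOQ, titre SD, effect size or expected share below LLOQ. The ranges used are SD 0.3 to 0.7 log10, effects from none to three-fold, and 10% to 90% of one-injection titres below LLOQ. The models are taken to be on the log10 scale. The 0.05 criterion is taken as two-sided, because its sidedness is not stated.

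**Analytic check.** With share c below LLOQ, the analysed mean moves per unit of true log10 mean by

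slope = 1 − c + (log10 2 / SD) × φ(z_c),

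where 1.00 means no distortion. At SD 0.5, log10 2 / SD = 0.602, so:
- c = 0.3: 0.70 + 0.602 × 0.348 = 0.91
- c = 0.5: 0.50 + 0.602 × 0.399 = 0.74
- c = 0.7: 0.30 + 0.602 × 0.348 = 0.51
- c = 0.9: 0.10 + 0.602 × 0.175 = 0.21

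At SD 0.3 the slope is 1.08 at 20%, 0.90 at 50% and 0.28 at 90%. At SD 0.2 it exceeds 1 up to 50%, so effects would be inflated there.

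**Simulation.** Planned adjuvanted cells, SD 0.5, true dose and adjuvant effects of 0.30 log10 in both schedules, ten-fold schedule effect, no true interaction, 500 runs per row. The last column is a left-censored normal regression with one common SD, correctly specified for these data.

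| Below LLOQ, 1 inj. / 2 inj. | LLOQ/2 dose effect, 1 inj. / 2 inj. | False dose × schedule | False adjuvant × schedule | Censored fit, same two tests |
|---|---|---|---|---|
| 10% / 0.1% | 0.300 / 0.297 | 5.8% | 4.6% | 6.2% / 4.8% |
| 30% / 0.6% | 0.270 / 0.298 | 5.8% | 4.6% | 6.8% / 5.2% |
| 50% / 2.4% | 0.218 / 0.299 | 12.4% | 8.8% | 6.6% / 5.4% |
| 70% / 7.3% | 0.148 / 0.299 | 29.0% | 25.6% | 5.0% / 3.8% |
| 90% / 24.3% | 0.057 / 0.279 | 71.8% | 66.2% | 6.6% / 4.8% |

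The one-injection column agrees with slope × 0.30: 0.273, 0.222, 0.153 and 0.063 for the last four rows.

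**Sensitivity of the false dose-by-schedule rate.**
- By SD: at 70% below LLOQ it runs from 52% (SD 0.3) to 17% (SD 0.7); at 90%, from 99% to 31%.
- With 1.5-fold effects at SD 0.5: 6%, 11% and 24% at 50%, 70% and 90%.
- With no true dose or adjuvant effect: 1% to 3% (2% to 4% for adjuvant by schedule), so no false interaction arises.

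**When the SD differs by schedule.** With SD 0.3 after one injection and 0.6 after two, true effects 0.20 (dose) and 0.30 (adjuvant), and 60% of one-injection titres below LLOQ:
- LLOQ/2 gives 0.15 and 0.22, with false interactions of 3% and 6%.
- A common-SD censored fit overshoots, at about 0.30 and 0.47, with 8% and 16%.
- A censored fit with an SD for each schedule gives 0.18 to 0.22 and 0.29 to 0.31, with 3% to 7%, across the settings run.

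The unadjuvanted two-injection arm (N=20) was left out because it exists only in Cohort 2. It could also have many values below LLOQ.

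**The case against.** The strongest reply has five parts.

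1. **The models are optional and the analyses descriptive** (Protocol 9.1). This stands. The point applies only if a linear titre model is run, and no confirmatory error rate is at issue. A 0.05 criterion would still decide which interactions are kept. The SAP names no particular interaction; the two schedule interactions are the ones exposed to this problem.

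2. **Heavy loss below LLOQ is assumed.** This stands too. Protocol 4.2 also allows that the peak response after one injection may be adequate, and expecting two injections to be needed says nothing direct about quantifiability.

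3. **The selection decision is past.** SAP 5.4 confines dose selection to the first interim and records a partial database lock, and SAP 5.7 says the formulation is no longer pursued. What remains is how effect modification is reported and interpreted.

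4. **Other planned outputs resist the floor.** Seroconversion does not depend on the substituted value. With baseline at LLOQ/2, a four-fold rise means a titre of at least 4 × LLOQ/2 = 2 × LLOQ, so the logistic model needs no value for post-dose results below LLOQ. This helps interpretation but does not repair the titre model. The GMTs carry the same floor, but as arm summaries they make no claim about interaction.

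5. **Censored regression can fail as well.** This is right for a common-SD fit, as shown above, and it is why the fix lets the SD differ by schedule. The reverse cumulative distribution curves cannot verify the assumed lower tail, because every value there is the same constant.

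**Conclusion.** The point holds conditionally. If roughly half or more of the one-injection titres are below LLOQ and dose or adjuvant effects are real, the LLOQ/2 linear models will usually understate those effects after one injection and can show schedule interactions that are absent on the log10 scale. At SD 0.5 with two-fold effects, the estimate keeps about 73% of the true dose effect at 50% below LLOQ (0.218/0.30) and about 19% at 90% (0.057/0.30). False dose-by-schedule findings rise from 12% to 72%. At about 30% or less the effect is small, and at a small SD the bias can reverse.

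A reader might infer that the substitution is certain to compress effects and create false interactions in this trial. The documents do not support that: they give no LLOQ, SD or share below LLOQ, and they only permit the models. Nor do they support the view that formulation selection still turns on this SAP text. The gap is that the plan has no method that holds up if the share proves high.

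**What to change.** In SAP 5.1.1.4, and wherever these models are reused for secondary endpoints, add that any linear titre model will be accompanied by a normal regression of log10 titre, left-censored at LLOQ, with the same covariates and interactions and with residual SD allowed to differ by schedule. Show both fits and base any effect-modification statement on the censored one. Report the share below LLOQ by arm and visit. Keep LLOQ/2 for the descriptive GMTs, fold-rises and reverse cumulative distribution curves. The same edit can align the scope of the rule in Protocol 9.4.2.1 with SAP 4.4.2.1.

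The cost is a sentence or two and one further procedure call, using a routine that permits a separate scale by schedule; no new data are needed. Because a partial lock has already taken place, record the addition in SAP 5.7 as made after it. The downside is reliance on normality of the unobserved lower tail, which cannot be verified from the curves and matters most when nearly all values are below LLOQ. Reporting the shares lets readers judge that.

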4.4.2.2 Fold-rise

The derived endpoint fold-rise is driven by both baseline and post-vaccination computed values as described in [Section 4.4.2.1](#) and is computed as individual titer ratio:

- Post-vaccination value divided by baseline value.

Note: If baseline or post-baseline is missing, then fold-rise is missing.

4.4.2.3 Seroconversion

The seroconversion endpoint is driven by both baseline and post-baseline computed values (assuming replicate values have been reduced to one value as described in Section 4.4.2.1) and a subject will have seroconverted if baseline values below LLOQ with detectable neutralization titer above assay LLOQ at D22, D36, D181 (Cohort 1) or D202 (Cohort 2), and at D366 (Cohort 1) or D387 (Cohort 2).

Note: If baseline or post-baseline is missing, then seroconversion is missing.

4.4.3 Cell-Mediated Immunity

4.4.3.1 Cell-Mediated Immunity Assessment Methods

Helper T cell type 1 (TH1) and Helper T cell type 2 (TH2) Cytokines will be collected for CMI analyses. TH1 cytokines include IFN-gamma (IFNg), Interleukin (IL)-2, IL-6, Tumor Necrosis Factor alpha (TNF α). TH2 cytokines include IL-4, IL-5, IL-10, IL-13. Additionally, Helper T cell type 17 (TH17) cytokine IL-17 and Granulocyte-macrophage-colony-stimulating Factor (GM-CSF)-producing T Helper (THGM) will also be collected and measured.

The list of cytokines is subject to be updated based on more information and knowledge on SARS-CoV-2 before the enrollment of participants of Cohort 2.

All cytokines above will be measured in whole blood following stimulation with pools of S-antigen peptides or full length S protein at D0, D22, and D36 for randomly selected participants from each study intervention group in Cohort 2.

Computed values for analysis

For each participant and each cytokine listed above, 3 measurements will be available for analysis. The 3 measurements are positive control, negative control, and spike stimulant. Each measurement has its own LLOQ and upper limit of quantification (ULOQ). Similar as described in [Section 4.4.2.1](#), the computational rule below is applied to the CMI measurements.

- If a value is < LLOQ, then use the computed value LLOQ/2
- If a value is between \geq LLOQ and < ULOQ, then use the value
- If a value is \geq ULOQ, then use the computed value ULOQ

Two subtractions will be calculated as below for each cytokine with computed values described above:

- Subtraction 1: (spike stimulant – negative control)
- Subtraction 2: (positive control - negative control)

Fold-rise

To derive the fold-rise of cytokines, the ratio of post-vaccination and baseline values of the corresponding subtractions above are used. Therefore, there are 2-fold rise ratios for each cytokine per participant per visit with CMI samples:

- Value of a post-baseline visit (spike stimulant – negative control) / baseline value of (spike stimulant – negative control)
- Value of a post-baseline visit (positive control – negative control) / baseline value of (positive control – negative control)

Note: If baseline or post-baseline computed value is missing, then fold-rise is missing.

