9.4.4 Exploratory Endpoint

9.4.4.1 Immunogenicity

Th1 and Th2 cytokines will be measured and summarized for individual and aggregate study arms.

Detailed CMI analyses will be defined in the SAP. The CMI analysis will be based on PPAS-CMI set.

The ratio between binding antibody (ELISA) concentration and neutralizing antibody titer will be summarized for individual and aggregate study arms. The ratio (neutralizing antibody / binding

antibody) will be calculated as difference in \log_{10} scale and with the 95% CIs calculated using normal approximation will be provided. The analyses will be performed on PPAS-IAS, unless otherwise specified.

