5.1.3 Statistical Methods for Exploratory Objective(s)

No hypotheses will be tested.

Ratio between binding antibody (ELISA) concentration and neutralizing antibody titer will be calculated and provided with 95% CI by intervention arm and main effects group. Analyses will be conducted on overall population and by age group.

Immunogenicity parameters for antibody persistence will be described with 95% CI for each age and vaccine group. The Reverse Cumulative Distribution Curves and distribution tables will also be produced in each age and vaccine group.

Last available neutralizing antibody titer and binding antibody (ELISA) concentration before infection will be described with 95% CI in aggregated vaccine group and aggregated placebo group.

Cell-Mediated Immunity

All cytokines collected will be summarized by visit.

TH1/TH2 ratios below will be summarized by treatment group on overall population and by age group for data collected at D22 and D36:

1. IFNg/ IL-4
2. IFNg/IL-5
3. IFNg /IL-13

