4. IL-2 /IL-4
5. IL-2 /IL-5

6. IL-2/IL-13
7. TNFa/IL-4
8. TNFa/IL-5
9. TNFa/IL-13

The ratios above are based on fold-rise as defined in [Section 4.4.3.1](#). That is for each cytokine, there are two Th1/TH2 ratios, one for each subtraction described in [Section 4.4.3.1](#). The ratio based on subtraction of spike stimulate – negative control will be used as main supportive information for Th1/Th2 results. Among all ratios listed, IFNg/IL-4 is the main TH1/TH2 ratio for characterizing Helper T cell polarization.

Post-vaccination antibody titers for the different study arms may be compared with human convalescent sera antibody titers, conditional to convalescent sample availability.

For descriptive purposes, the statistics presented on [Table 5.1](#) will be produced.

A principle component analysis (PCA) will be performed on collected CMI data to identify linear combinations, i.e., principle components, of the biological variables. PCA analyses will be conducted for the two subtractions described in [Section 4.4.3](#), separately. All cytokines will be involved in the PCA analysis. The variables were \log_{10} -transformed and centered to 0 mean and scaled to the standard deviation; the covariance matrix will be used and for each analysis two principal components (PC1 and PC2) will be extracted accounting for a given proportion of data variability. Each component will be characterized by its loadings, i.e., weights quantifying how much each original variable contributes to the component. PCA will be applied to PPAS-CMI analysis set.

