5.3.4 Cell-Mediated Immunity

The values will be reported as recorded.

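### SAP 4.4.3.1 has no rule for a background-subtracted cytokine value of zero or below, so CMI fold-rises and the main IFNg/IL-4 ratio can be undefined, wrong-signed or spuriously positive

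*SAP*

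**What the plan says.** Protocol 9.4.4.1 leaves the method to the SAP: "Detailed CMI analyses will be defined in the SAP".

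SAP 4.4.3.1 has three readings per cytokine (positive control, negative control, spike stimulant) and notes that "Each measurement has its own LLOQ and upper limit of quantification (ULOQ"). It then sets this order:

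1. Replace a reading below its LLOQ by LLOQ/2, and one at or above its ULOQ by the ULOQ.
2. Subtract the negative control from the spike reading, and separately from the positive control.
3. Form the fold-rise. For spike this is "Value of a post-baseline visit (spike stimulant – negative control) / baseline value of (spike stimulant – negative control"; the positive-control version has the same form.

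The single exception is "Note: If baseline or post-baseline computed value is missing, then fold-rise is missing". SAP 5.3.4, the CMI entry under missing data and outliers, says only "The values will be reported as recorded".

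SAP 5.1.3 lists nine TH1/TH2 ratios. It says "The ratios above are based on fold-rise as defined in" SAP 4.4.3.1, and makes the spike-based version the main supportive result. It adds: "Among all ratios listed, IFNg/IL-4 is the main TH1/TH2 ratio for characterizing Helper T cell polarization". It also plans a PCA for each of the two subtractions, with log10-transformed variables.

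**The concern.** A half-LLOQ rule normally guarantees a positive denominator. It does so for the antibody fold-rise in SAP 4.4.2.1 and 4.4.2.2, where substitution is the last step before division. For CMI the same rule comes one step too early: the subtraction follows it and can return zero or a negative number. Nothing later in the SAP catches that.

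The weak point is the denominator. Baseline is measured in people chosen because they show no evidence of prior SARS-CoV-2 exposure (Protocol 4.2, study population), so a baseline spike reading close to background is plausible.

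Undefined values will stop a program and be noticed. The more troublesome case is a quotient of two negatives, which is positive, passes any later log10 step and looks valid. Without a written rule, dropping, replacing or keeping such values is left to programming, and the choice can change the reported helper T cell polarization.

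**Working it through.** **The plan's own figure.** The CMI subset (Protocol Table 4.2 note) is 2×18 + 4×6 = 60 younger and 2×9 + 3×3 = 27 older participants, 87 in total. This reproduces.

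**What the written rule returns.** The readings below are illustrative.

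| Baseline difference | Post difference | Fold-rise | What happened |
|---|---|---|---|
| 4-6 = -2 | 50-5 = 45 | -22.5 | a rise, shown as negative |
| 4-6 = -2 | 3-8 = -5 | +2.5 | a fall, shown as a rise |
| 0.5-0.5 = 0 (both readings below an equal LLOQ of 1) | 9.5 | 9.5/0 | undefined |
| 0.5-1 = -0.5 (spike LLOQ 1, negative-control LLOQ 2, both readings below) | any | sign flipped | sign set only by the assay limits |

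**At ratio level.** IFNg/IL-4 uses four differences. Take IFNg at -22.5 and IL-4 at (6-3)/(2-3) = -3. The ratio is -22.5/-3 = +7.5, an apparent TH1 skew built from two invalid fold-rises.

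The direction can also reverse. With LLOQ 1, let the IFNg baseline be 1.5-2 = -0.5 and the post value 1-6 = -5, a fold-rise of +10. With an IL-4 fold-rise of 2 the ratio is 5. If both IFNg differences are replaced by LLOQ/2 = 0.5, the IFNg fold-rise is 1 and the ratio is 0.5.

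**PCA.** Log10 does not exist at or below zero, so any such subtraction cannot enter.

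**How often.** The documents give no LLOQs, well variability or baseline levels. Assume independent wells, none below LLOQ, with within-well SD s on the log10 scale, and let r be the true ratio of baseline spike to background. Then P(difference ≤ 0) = Φ(-log10 r / (s√2)).

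| r | s = 0.10 | s = 0.25 |
|---|---|---|
| 1 | 0.50 | 0.50 |
| 1.6 | 0.074 | 0.282 |
| 2 | 0.017 | 0.197 |
| 3 | 0.000 | 0.089 |

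Readings below LLOQ would move these rates in either direction, depending on which well has the higher limit.

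**Small groups.** CMI groups within an age stratum have 3, 6, 9 or 18 members. If 10% of baseline differences were at or below zero (an assumption), the chance of at least one in a group, 1 - 0.9^n, would be 27%, 47%, 61% and 85%.

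**The case against.** The strongest reply is that little hangs on this. CMI is exploratory, covers 87 people and tests no hypothesis, and SAP 5.1.2.4 says the formulation is no longer investigated further. That stands and sets the size of the point.

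Some of the errors are also visible. When both fold-rises are negative, a table of fold-rises would show it. That stands too, but when both IL-4 differences are negative the fold-rise and the ratio both look valid.

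A reader might go further in four ways that the documents do not support:

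- That a particular number of participants will have unusable ratios. This depends on assumed variability, assumed baseline signal, independence between cytokines and the course of IL-4 after vaccination, none of which is given.
- That formulation selection was distorted. SAP 5.4 lists the CMI analyses (not the PCA) for the first interim, alongside primary immunogenicity and safety. Nothing shows how the ratios were weighed or how values at or below zero were handled.
- That the geometric means of SAP Table 5.1 also fail. The relevant row carries a footnote missing from the available text, so its scope for CMI is unknown.
- That cytokine levels offer an untouched fallback. SAP 5.1.3 says "All cytokines collected will be summarized by visit" but not whether those are raw or subtracted values.

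A replacement limit also has a cost, since it makes some ratios depend on assay limits, and describing a difference instead of a ratio would avoid division. Any single stated rule would close the gap; a positive limit keeps the outputs the SAP already plans.

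**Conclusion.** The point holds. Followed literally, SAP 4.4.3.1 gives undefined, wrong-signed or spuriously positive fold-rises whenever a background-subtracted value is zero or below, and SAP 5.1.3 carries them into all nine TH1/TH2 ratios and the PCA. That follows from the order of the steps and needs no assumption. The positive-control subtraction has the same formal gap but should reach zero less often.

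The frequency does rest on assumptions: about half of baseline differences per cytokine if spike equals background, falling towards zero as baseline signal rises. The reach is limited to exploratory, descriptive CMI outputs; the primary and secondary endpoints are untouched. It should still be fixed, because IFNg/IL-4 is the named summary of polarization and the rule as written can report a false value for it.

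**What to change.** In SAP 4.4.3.1, add one rule applied after the subtraction and before any ratio or log10 step: a difference below a stated positive limit, for example half the LLOQ of the stimulated well for that cytokine, is replaced by that limit. Apply it to every difference below the limit, not only those at or below zero; otherwise a tiny positive difference would stay lower than a replaced negative one. Use the same values for fold-rise, TH1/TH2 ratios and PCA, and report the number replaced by cytokine, group and visit.

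Show the TH1/TH2 summaries with and without ratios that have a replaced baseline, because those depend on the LLOQs. With both baselines replaced at LLOQ/2 and post values of 50 (IFNg) and 5 (IL-4), the ratio is (50/5) × (IL-4 LLOQ / IFNg LLOQ). Assumed LLOQs (IFNg, IL-4) of (10,1), (1,1) and (1,10) give 1, 10 and 100. With only IFNg replaced (LLOQ 1) and an IL-4 fold-rise of 5/2 = 2.5, limits of 0.25, 0.5 and 1 give 80, 40 and 20.

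If interim CMI data have already been reviewed, label the rule post hoc in the SAP and the report.

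The cost is SAP wording and re-running one derived dataset, plus any interim outputs already produced; no new samples are needed. The price in the data is ties, LLOQ dependence and some genuine small positive differences overwritten.
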